## 9 SAFETY REPORTING

### 9.1 Section 10 WMO event

In accordance to section 10, subsection 1, of the WMO, the investigator will inform the subjects and the reviewing accredited METC if anything occurs, on the basis of which it appears that the disadvantages of participation may be significantly greater than was foreseen in the research proposal. The study will be suspended pending further review by the accredited METC, except insofar as suspension would jeopardize the subjects' health. The investigator will take care that all subjects are kept informed.

## 9.2 AEs and SAEs

### 9.2.1 Adverse events (AEs)

Adverse events are defined as any undesirable experience occurring to a subject during the study, whether or not considered related to the experimental intervention. All adverse events reported spontaneously by the subject or observed by the investigator or his staff will be recorded.

### 9.2.2 Serious adverse events (SAEs)

A serious adverse event is any untoward medical occurrence or effect that:

- results in death;
- is life-threatening (at the time of the event);
- requires hospitalization or prolongation of existing inpatients' hospitalization;
- results in persistent or significant disability or incapacity;
- is a congenital anomaly or birth defect;
- Any other important medical event that may not result in death, be life threatening, or require hospitalization, may be considered a serious adverse experience when, based upon appropriate medical judgment, the event may jeopardize the subject or may require an intervention to prevent one of the outcomes listed above.

According to the guidelines of the Dutch Association of Gastroenterology and Hepatology, adverse events will be categorized as follows:

Slight: no (prolongation of) admission, no intervention, no change in scheduled surgical operation date;

Mild: (prolongation of) admission less than 4 days, otherwise as mentioned under "slight"

NL51461.078.15 / NCT02328664 Scar biopsies after malignant colorectal polypectomy of uncertain radicality

Moderate: (prolongation of) admission less than 11 days, and/or transfusion of no more than 4 units of blood and/or endoscopic or percutaneous (non angiographic) intervention, and/or delay of the scheduled surgical operation.

Serious: (prolongation of) admission of more than 10 days, and/or transfusion of more than four units of blood, and/or angiographic intervention and/or intensive care admission and/or antedating or cancellation of the scheduled surgical operation, and/or death.

Although not specifically addressed in previous studies, the risk of taking biopsies from a healed polypectomy wound is considered virtually zero, as is our own experience as well. It is even unnecessary to discontinue systemic anticoagulants such as coumarins or double thrombocyte aggregation inhibition.

The risk of as sigmoidoscopy and colonoscopy are roughly the same and are associated with polypectomy, which can cause perforation and bleeding, both immediately or delayed. In a mixed population of diagnostic and therapeutic colonoscopies, both are approximately one to two in 1000 procedures. The intent of the investigational procedures in this study is only to take biopsies. The risk if the investigational procedure is to our best guess considered very small, less than 1 out of 5000.

All patients will be followed for ninety-two days after the operation to assess for (S)AE's. In case of any suspected (S)AE, all appropriate medical action will be taken to ensure damage control from the patient's health perspective. There is a 7 x 24 service at the participating centers, which is easy amendable to the trial subjects in case anything might happen.

The trial center will report the (S)AEs through the web portal "*ToetsingOnline*" to the accredited METC that approved the protocol, within 15 days after the trial center has first knowledge of the serious adverse events.

SAEs that result in death or are life threatening should be reported expedited. The expedited reporting will occur not later than 7 days after the responsible investigator has first knowledge of the adverse event. This is for a preliminary report with another 8 days for completion of the report.

### 9.2.3 Suspected unexpected serious adverse reactions (SUSARs)

Not applicable (no investigational product)

### 9.3 Annual safety report

Not applicable (no investigational product)

#### 9.4 Follow-up of adverse events

All AEs will be followed until they have abated, or until a stable situation has been reached. Depending on the event, follow up may require additional tests or medical procedures as indicated, and/or referral to the general physician or a medical specialist.

SAEs need to be reported till end of study within the Netherlands, as defined in the protocol

#### 9.5 Safety Committee

A Data Safety Monitoring Board is not needed. Adverse events will be reported to the trial center and the safety committee. This committee consists of [name] [name], orthopedic surgeon and head of the scientific committee at the Deventer Hospital, and [name] [name], epidemiologist at the Deventer Hospital. They will be informed about adverse events after the endoscopic procedures and may decide to take specific measurements such as detailed examination of the AE.

## **10 Statistical analysis**

All statistical analyses will be done in the Deventer Hospital, with support of the local department of clinical epidemiology ([name]). Final approval will be obtained from the department of biostatistics and epidemiology at the Erasmus Medical Center ([name]). In principle, sensitivity will be calculated by dividing the number of patients with positive biopsies by the number of patients with tumor in the bowel wall and / or resected lymph nodes. Separate analysis will be done for bowel wall affection (as opposed to lymphatic spread) only.

The above-mentioned factors of potential influence will be studied on associations with the presence or absence of tumor in the bowel wall and / or resected lymph nodes. This will be done by using an independent samples *t*-test in the case of continuous normally distributed variables; by nonparametric test (e.g. Mann-Whitney U-test) in case of non-normally distributed ordinal variables; by Chi-Square statistics in case of categorical variables and by multiple logistic regression to investigate multiple associations.

Missing data will be dismissed from the analysis: the main issue is, whether there are preoperative biopsies and a resection specimen. If one of both fails, the loss will be compensated by the inclusion of another patient, as long as the number of evaluable patients is not reached.

NL51461.078.15 / NCT02328664 Scar biopsies after malignant colorectal polypectomy of uncertain radicality

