### 2.2 Secondary Objectives:

[figure not shown]
- 90-day mortality after rescue surgery: the number of patients that died within 91 day after the operation for presumed residual adenocarcinoma
- The sensitivity of biopsies for residual cancer in the bowel wall: the number of patients with endoscopic biopsies containing adenocarcinoma divided by the number of patients with adenocarcinoma in the resected bowel wall (regardless of regional lymph nodes)
- The number of complications (defined according to GCP and the Dutch Association of Gastroenterology) after biopsies from the polypectomy: the number of patients with bleeding or perforation after taking biopsies from the polypectomy scar, requiring at least prolongation of treatment, or admission to hospital, or delay or speeding up rescue surgery. This up until the moment of surgery.
- The sensitivity of global endoscopic assessment of initial polypectomy as well as scar biopsies for residual cancer: the number of patients in whom the endoscopic resection was assessed as incomplete and who also have residual cancer in the surgically resected specimen divided by the total number of patients in whom the endoscopic resection was judged to be incomplete.
- The proportion of patients with residual cancer in the resected specimen if malignancy was unsuspected during the endoscopic polypectomy: the number of patients in whom the malignancy was initially unsuspected during endoscopic polypectomy and who also have residual cancer in the surgical specimen divided by the total number of patients in whom the malignancy was initially unsuspected during endoscopic polypectomy.
- The proportion of patients in whom exclusion criteria apply and the results of surgery / complications of surgery in these patients.

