#### 4.4 Sample size calculation

The overarching goal is to investigate whether second-look endoscopic biopsies after resection of a malignant polyp with uncertain pathological completeness can be used as a screening instrument to aid in the clinical decision whether rescue surgery should be performed or not. The specificity of second-look biopsies from the polypectomy site for residual malignancy is estimated to be near 100%, as it is reasonable to state that no person without residual malignancy in the bowel wall is likely to have tumor in second look biopsies, in other words, the false-positive rate will be approximately zero.

Accordingly, sample size calculations will be done on the basis of sensitivity, i.e. the number of patients with positive second-look biopsies divided by the number of patients who do have residual tumor in the resected specimen. We state that sensitivity should be at least 95% to be clinically relevant. A non-inferiority approach can be used to calculate sample size. In that case, the null-hypothesis states that sensitivity is significantly inferior to 95%. Because proof of exact equality to 95% is impossible, a pre-stated margin of non-inferiority of -5% (90% in our study) is accepted.

The distributions of the probabilities belonging to the null- (around  $p = 0.90$ ) and alternative (around  $p = 0.95$ ) hypothesis is binomial but may be approximated by a normal distribution for sample size calculation.

Using the normal approximation, it can be calculated that 184 patients need to be included to achieve a power of 0.80 with and a probability of falsely accepting biopsies as non-inferior ( $\alpha$ ) of 0.05.

Using binomial distributions, it can be shown that 194 patients need to be included to achieve this goal. We will use the latter number for a robust estimate of sample size.

We estimate incomplete data and / or refusal to participate in 1 out of 10 patients invited.

This calculates to a number of 216 patients with residual tumor to be invited. Depending on the prevalence of residual tumor, which is estimated to vary between 10 and 30% (average 20%) of all patients, a total of 1080 patients fulfilling the inclusion criteria need to be invited to accomplish this number.

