### 8.3.2 Investigational biopsies

Biopsies will be taken through the endoscope with a standard biopsy forceps. The number of biopsies depends on the size of the lesion / scar. In case of a small scar, the neo-epithelial surface of the lesion should be removed by biopsies. However, if more than ten biopsies would be necessary to do this, five biopsies will be taken from the center in a mesh-like fashion at approximately 5 mm intervals. In addition, biopsies will be taken from the edge (if discernible) at 5 mm intervals. Any mucosal irregularities in or around the scar will be biopsied separately. Biopsies should be collected according to pathology standards in formalin.

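### The sensitivity formula does not restrict its numerator to specimen-positive patients, so any patient with positive biopsies and a clean specimen inflates the result

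*Protocol*

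**What the plan says.** The protocol gives the biopsy sensitivity as a ratio in three places.

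- Section 10: "sensitivity will be calculated by dividing the number of patients with positive biopsies by the number of patients with tumor in the bowel wall". The sentence continues so that tumor in resected lymph nodes also counts in the denominator. A separate bowel-wall analysis is planned.
- Section 4.4: "the number of patients with positive second-look biopsies divided by the number of patients who do have residual tumor in the resected specimen".
- Section 2.2, for the bowel wall alone: "the number of patients with endoscopic biopsies containing adenocarcinoma divided by the number of patients with adenocarcinoma in the resected bowel wall".

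Section 4.4 expects specificity near 100% because "no person without residual malignancy in the bowel wall is likely to have tumor in second look biopsies". It sets the requirement thus: "We state that sensitivity should be at least 95% to be clinically relevant", and then "a pre-stated margin of non-inferiority of -5% (90% in our study) is accepted".

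On how the biopsies are taken, Section 8.3.2 says: "In case of a small scar, the neo-epithelial surface of the lesion should be removed by biopsies". If more than ten biopsies would be needed for that, the scar is sampled at intervals instead.

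No section says how a patient with positive biopsies and a clean specimen is classified.

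**The concern.** Sensitivity is a proportion: its numerator must be a subset of its denominator. Read literally, the three definitions put every biopsy-positive patient in the numerator and only specimen-positive patients in the denominator. A patient with positive biopsies and a clean specimen then adds one above the line and nothing below it.

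The near-zero false-positive argument in Section 4.4 does not close this gap. It covers people who have no residual malignancy. It does not cover a patient who had a small residual focus that the biopsies themselves removed. The instruction for small scars makes such a patient possible.

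The separate bowel-wall analysis has a second route to the same error. A biopsy-positive patient with a clear wall but positive nodes would count in the numerator only.

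The excess pushes towards declaring the biopsies adequate, and that conclusion would support omitting surgery after negative biopsies. The gap between the null (90%) and the target (95%) is only five points, so a few patients matter.

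**Working it through.** **Inputs from Section 4.4.** Null p0 = 0.90, alternative p1 = 0.95, alpha 0.05, power 0.80, and 194 patients with residual tumor. Sidedness is not stated.

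**The plan's own figures.** With one-sided alpha,

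n = [(1.645·√(0.90·0.10) + 0.842·√(0.95·0.05)) / 0.05]² = 183.3, so 184, as stated.

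A two-sided alpha gives 239 and does not fit. At n = 194 the exact binomial rule is success at 182 or more. Its alpha is 0.043 and its power 0.824, so 194 meets the stated goal. Then 194/0.9 = 215.6, so 216, and 216/0.20 = 1080. These figures are not in dispute. The cut-off of 182 is derived here; the protocol does not print it.

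**The ratios.** Let D be the specimen-positive patients, TP those of them with positive biopsies, and k the patients with positive biopsies and a clean specimen.

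- As written: (TP + k)/D
- Specimen as reference: TP/D
- Composite reference (tumor in biopsy or specimen): (TP + k)/(D + k)

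The written ratio exceeds the specimen-reference ratio by k/D. With D = 194, that is 1/194 = 0.52 percentage points per discordant patient.

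**Fixed k, with TP/D at the null of 90% (TP = 174.6); k is assumed.**

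| k | As written | Specimen reference | Composite | Chance of reaching 182, as written |
|---|---|---|---|---|
| 0 | 90.0% | 90.0% | 90.0% | 0.043 |
| 2 | 91.0% | 90.0% | 90.1% | 0.117 |
| 5 | 92.6% | 90.0% | 90.3% | 0.334 |
| 10 | 95.2% | 90.0% | 90.5% | 0.775 |
| 20 | 100.3% | 90.0% | 90.9% | 0.998 |

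**Random clearance; c is assumed.** Suppose biopsies detect 90% of all patients with residual tumor, and a fraction c of the detected foci is cleared from the specimen. Inclusion runs until 194 patients are specimen-positive. Node-only patients are left out.

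- Probability that a residual case is specimen-positive: 1 − 0.9c
- Expected written ratio: 0.9/(1 − 0.9c)
- Strict sensitivity: s = 0.9(1 − c)/(1 − 0.9c)
- Expected k: 194·0.9c/(1 − 0.9c)

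The chance of passing sums P(k)·P(Binomial(194, s) ≥ 182 − k) over k, where k is negative binomial.

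| c | Expected k | Mean written ratio | Chance of passing, as written | Chance of passing, strict numerator |
|---|---|---|---|---|
| 0% | 0 | 0.900 | 0.043 | 0.043 |
| 1% | 1.8 | 0.908 | 0.11 | 0.039 |
| 2% | 3.6 | 0.917 | 0.21 | 0.036 |
| 3% | 5.4 | 0.925 | 0.34 | 0.033 |
| 5% | 9.1 | 0.942 | 0.60 | 0.027 |

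With the strict numerator the chance of false acceptance stays at or below 0.043 in every row.

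**The case against.** The best defense is that this is the ordinary measure, loosely worded. Sections 2.1 and 8.1.1 set the biopsies against the surgical specimen. A binomial sample size makes sense only if the positives are a subset of the denominator. Table 1 in Section 8.7 counts by patients with residual cancer at operation and annotates its first limits as all being positive. Section 10 also says that its formula holds in principle. A reader might therefore infer either that the analysts mean to use an unrestricted numerator or that nothing is wrong. Neither follows. The subset was probably intended, but no section writes it for the biopsies, while two other items in Section 2.2 (endoscopic judgment of completeness, and unsuspected malignancy) do spell out the joint condition.

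A second objection is that discordant patients may be rare. That stands. Section 8.3.2 makes clearance possible, not likely. It concerns the surface of small scars, larger scars are only sampled, and residual tumor may lie deeper, since a vertical margin under 1 mm is one way to qualify. A reader might infer that the trial will report a sensitivity above 100%. At a true 90% that takes about 20 discordant patients per 194, and nothing in the protocol suggests so many.

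Third, node-only patients enter the primary denominator although scar biopsies cannot be expected to find them. This pulls the primary ratio down relative to bowel-wall sensitivity, so the net direction against that measure is not established. It does not remove the k/D excess.

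Finally, both pathology results are recorded for each patient (Sections 8.1.3.5 and 8.1.3.7), so a correct estimate can still be computed. That limits the damage. It does not excuse a formula that the protocol itself fixes three times.

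**Conclusion.** The point holds as a defect in the written definition of the primary measure. Whenever a biopsy-positive patient has a clean specimen, the formula overstates sensitivity against the specimen by 0.52 percentage points per such patient at D = 194, towards a false claim of adequacy. About ten such patients would turn 90% into a reported 95%.

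How large the error would be in practice is unknown, because the protocol gives no clearance rate. At zero there is no bias. At 1% the mean shift is 0.8 points, yet the chance of false acceptance still rises from 0.043 to 0.11; at 5% it reaches 0.60. These figures assume one-sided testing at 182 of 194, no node-only patients, and clearance only among detected foci.

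The protocol does not support saying that clearance is likely, or that a composite reference must be primary. The latter would put the index test into its own reference standard and depart from the comparator that the protocol names.

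**What to change.** In Sections 2.2, 4.4 and 10, define the numerator as patients positive on both the scar biopsies and the resected specimen, and the denominator as patients with tumor in the resected specimen. For the bowel-wall analysis, use the bowel wall in both. State that the counts in Section 8.7 and Table 1 follow the same definition; under the Section 10 formula, early-stopping limits would also be reached too easily.

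Report the number of patients with positive biopsies and a clean specimen. Pre-specify the composite-reference estimate, with tumor in biopsy or specimen counted in both numerator and denominator, as a sensitivity analysis.

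The cost is wording in four sections; no new data are needed and the sample size stands. There are two downsides. The reported sensitivity becomes slightly less favorable. The strict estimate also counts foci removed by biopsy in neither numerator nor denominator, so it sits a little below the composite: 0.895 against 0.900 at 5% clearance, from 0.9·0.95/(1 − 0.045).

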## Summary

**Rationale:** colorectal polyps may harbor adenocarcinoma. Numbers are increasing due to the nationwide colorectal screening program. After endoscopic removal, rescue surgery is often performed because radicality can not be guaranteed by the pathologist. However, in 85% of surgical specimen no residual malignancy is found. Given morbidity and mortality associated with surgery a method to diagnose residual cancer is needed.

Biopsies from the polypectomy site are variably used to reduce the likelihood of residual tumor at the polypectomy site under these circumstances. However, the sensitivity of such biopsies is unknown.

Many patients are operated upon because of risk factors for dissemination such as lymphovascular invasion, despite a radical local resection. There has never been a prospective registration of these patients with regard to surgical outcome.

**Objectives:** 1 to evaluate the sensitivity of second-look endoscopic biopsies from the polypectomy site for residual tumor. 2. To register patients who do not fulfill inclusion criteria in order to evaluate their surgical outcomes.

**Study design:** prospective cross-sectional design using a multi-center approach.

**Study population:** patients in whom a malignant colonic polyp has been removed. For the biopsy part of the study (1) they should be planned for rescue surgery (including transmural excision) for the sole reason of (potentially) irradical endoscopic resection of a colorectal adenocarcinoma without poor differentiation, lymphovascular invasion or tumor budding and without other signs of dissemination.

**Intervention (biopsy part of the study):** endoscopic biopsies from the polypectomy site before operation. Patients who are excluded will only be registered.

**Main study parameters/endpoints:** Biopsy part of the study: sensitivity of second-look biopsies from the polypectomy site for residual tumor in the resected bowel and postoperative mortality. Various other factors will be assessed that might be associated with residual cancer. Observational part of the study: The prevalence of patients with exclusion criteria and outcome of surgery in this group (observational part of the study).

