### 4.2 Inclusion criteria (biopsy part of the study)

In order to be eligible to participate in this study, a subject must meet all of the following criteria:

- Aged 18 or above.
- Endoscopically removed colorectal lesion with the following pathological characteristics:
  - A moderately-to-well differentiated adenocarcinoma.
  - If possible to judge: distance between adenocarcinoma and vertical or lateral resection margin is less than 1 mm.
  - In case of piecemeal resection: radicality cannot be assessed (mostly due to loss of orientation and multiple fragments).
  - Absence of / not assessable lymphatic / vascular invasion.
  - No tumor budding (only if specifically mentioned in the pathology report).
  - No deep submucosal invasion (> 1 mm)

- No suspicion of dissemination on the following investigations: serum carcino-embryonic antigen, a computer tomographic (CT) scan of the abdomen and a chest X-ray; in case of a rectal tumor (less than 15 cm from the anal verge): an additional magnetic resonance imaging of the rectum.
- Operation or endoscopic full-thickness resection (including Transanal Endoscopic Microsurgical excision (TEM), Transanal Minimal Invasive Surgery (TAMIS) or Endoscopic Full-thickness Resection (eFTR)) is advised in agreement with the Dutch Guideline on Colorectal cancer, planned and agreed on by the patient.
- Written informed consent is obtained.

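### The primary sensitivity has two denominators (resected bowel, or bowel wall and/or lymph nodes), and the hypotheses and the 194 cases make no allowance for node-only disease

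*Protocol*

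**What the plan says.** - **Summary, main study parameters:** "sensitivity of second-look biopsies from the polypectomy site for residual tumor in the resected bowel".
- **Section 10:** the main calculation divides patients with positive biopsies "by the number of patients with tumor in the bowel wall and / or resected lymph nodes". It then adds: "Separate analysis will be done for bowel wall affection (as opposed to lymphatic spread) only".
- **Section 2.2:** a secondary objective is sensitivity against "the number of patients with adenocarcinoma in the resected bowel wall (regardless of regional lymph nodes"). Listing this as secondary implies that the primary version counts nodes.
- **Sections 2.1, 4.4 and 8.1.1:** these refer to the surgical or resected specimen and do not say whether nodes belong to it. Section 10.1 only points back to 8.1.1.
- **Section 4.4:** the specificity argument is framed on the wall: "no person without residual malignancy in the bowel wall is likely to have tumor in second look biopsies". Sensitivity is to be at least 95%, with 90% as the null value, and 194 patients with residual tumor are required.
- **Section 4.2:** the reference resection may be a local one: "Operation or endoscopic full-thickness resection (including Transanal Endoscopic Microsurgical excision (TEM"), TAMIS or eFTR.
- **Section 1:** nodal disease is described as rare in low-risk lesions, without a figure.

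**The concern.** Two patients can both be counted as having residual tumor under Section 10 and yet be quite different for this test. One has carcinoma in the scar, which a biopsy can find. The other has a clean wall and a positive node, which a scar biopsy cannot find. Section 4.4's own reasoning, that people without tumor in the wall will not have positive biopsies, makes the second patient a near-certain false negative, however well the biopsies are taken.

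The distance between 95% and 90% is small, so a few such patients matter. Section 4.4 does not mention them.

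The second issue is that the reference standard differs by procedure. Node-only disease can be counted only where nodes are removed and examined. The protocol provides no node assessment for TEM, TAMIS or eFTR, and its planned follow-up ends 92 days after the operation (Section 9.2.2). Under the combined definition, the result therefore depends partly on the mix of resections, which the protocol does not control. The association analyses in Section 10 use the same combined outcome.

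**Working it through.** **Inputs from Section 4.4.** Null 0.90, alternative 0.95, alpha 0.05, power 0.80, 194 evaluable cases, 10% loss, residual tumor in 10 to 30% (average 20%).

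**Reproducing the plan.** The normal approximation with one-sided alpha gives

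n = [(1.645·√(0.90·0.10) + 0.842·√(0.95·0.05)) / 0.05]² = 183.3, rounded up to 184.

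With the exact binomial at n = 194, success needs at least 182 positives. The type I error is then 0.043 and power at 0.95 is 0.824. Further, 194/0.90 gives 216, and 216/0.20 = 1080. All the stated figures hold.

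**Room for misses.** Success allows 194 − 182 = 12 negatives. A true sensitivity of 95% already uses 194 × 0.05 = 9.7 of them on average.

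**Effect of node-only cases.** Let q be the share of included patients with node-only disease (assumed) and w the share with tumor in the wall (20%, taking the plan's average as wall prevalence). Then

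- node-only share of the denominator: f = q/(w + q)
- apparent sensitivity = wall sensitivity × (1 − f)
- power = P(X ≥ 182), with X binomial (194, apparent sensitivity)

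| q | f | Apparent sensitivity (wall 95%) | Power (wall 95%) | Power (wall 98%) |
|---|---|---|---|---|
| 0 | 0 | 95.0% | 0.82 | – |
| 0.2% | 0.99% | 94.1% | 0.63 | 0.99 |
| 0.5% | 2.4% | 92.7% | 0.33 | 0.91 |
| 1% | 4.8% | 90.5% | 0.07 | 0.47 |

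Across the plan's prevalence range, q = 0.5% with 95% wall sensitivity gives power 0.07 at 10% prevalence and 0.49 at 30%.

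**Effect of local excisions.** Let L be the share of local excisions, assumed unrelated to where the tumor lies. Take a true node-only share of f = 5% and wall sensitivity of 95%. The observed share is f(1 − L)/(1 − Lf).

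| L | Observed share | Apparent sensitivity | Power |
|---|---|---|---|
| 0 | 5.0% | 90.3% | 0.05 |
| 25% | 3.8% | 91.4% | 0.14 |
| 50% | 2.6% | 92.6% | 0.31 |
| 75% | 1.3% | 93.8% | 0.57 |

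The same biopsy performance and the same disease give different primary results, depending only on the procedure mix.

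**With a wall-only denominator.** 194 wall-positive patients give power 0.82. If 194 were collected on the combined definition and 5% were node-only, 194 × 0.95 ≈ 184 wall-positive cases remain. Success then needs at least 173, and power is 0.79. Keeping 194 wall-positive cases would take 194/0.95, rounded up to 205 combined cases, or about 205/0.90/0.20 = 1139 invited instead of 1080.

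**The case against.** The combined denominator may be deliberate. Section 4.4 states the goal as helping to decide on rescue surgery, Section 8.7 weighs residual tumor against postoperative death, and Section 1 says nodal disease is a concern even with normal imaging. For that decision, a negative scar biopsy with a positive node is a real miss, and a wall-only headline would look more favorable. This stands as a reason to report node-only disease prominently. It does not reconcile the Summary with Section 10, or supply hypotheses set for the combined endpoint. If the 95% is meant for that endpoint, the wall sensitivity required is 0.95/(1 − f): 97.9% at f = 3% and 100% at f = 5%.

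The contradiction is also milder than it first looks. Sections 2.2 and 10 agree with each other, the Summary's wording is less explicit than Section 2.2's, and the bowel-wall phrase in Section 4.4 belongs to the specificity argument, not to the definition of sensitivity. The wall-only estimate is already planned, although as a secondary analysis it cannot replace the primary test.

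Two stronger readings are tempting. A reader might infer that the trial is likely to fail even if biopsies work as assumed. The documents do not support this: they give no node-only rate, the inclusion criteria remove known high-risk lesions, and Section 4.4 asks for at least 95%, with much less loss at 98%. A reader might also infer that local excisions contribute to failure. The direction is the opposite: unseen node-only cases leave the denominator and raise apparent sensitivity.

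**Conclusion.** The point holds as an inconsistent definition of the primary endpoint, together with a sample size that makes no allowance for node-only cases. The size is conditional. At 20% wall prevalence and exactly 95% wall sensitivity, node-only disease in 1 of 200 included patients would reduce power from 0.82 to 0.33; at 98% wall sensitivity it would leave 0.91. The node-only rate and the wall sensitivity are both assumptions.

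The unequal reference standard is a separate defect. It biases apparent sensitivity upward as the share of local excisions grows. Neither defect shows that the combined endpoint is illegitimate. They show that one denominator must be named, that every patient's reference must be able to establish it, and that the benchmarks and the count must belong to it.

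**What to change.** 1. Name adenocarcinoma in the bowel wall of the resected specimen as the primary denominator in the Summary and Sections 2.1, 2.2, 4.4, 8.1.1 and 10. Every eligible reference resection can show it.
2. Count the 194 cases, and the case numbers in Table 1 of Section 8.7, on wall-positive patients.
3. Keep the wall-and/or-node sensitivity as a secondary analysis, restricted to patients with examined nodes.
4. Report the node-only rate, among patients with examined nodes, beside the primary result, because it bears on the decision about surgery.
5. If the sponsor deliberately wants the combined endpoint as primary, restate the power and the 95% and 90% benchmarks with an explicit node-only share, and restrict that endpoint to patients with examined nodes.

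**Cost.** Mostly wording: both analyses are already planned, and node counts are already recorded (Section 8.1.3.7). The primary claim would be limited to local residual tumor. If cases have been counted on the combined definition, the wall-positive number is slightly lower (184 of 194 at a 5% node-only share, power about 0.79). That should be stated, or covered by the modest extra recruitment shown above.
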